3.6 Design of the clinical investigation

3.6.1 General information

The is a comparator-controlled, randomised, double-blinded clinical intervention study designed to yield reliable, high-quality, and medical-device regulation compliant evidence. The study aims to assess the effects of a novel digital intervention, MEL-T01, on the symptoms of MDD. MEL-T01 has no prior equivalent devices. The closest equivalent is AKL-T01 (Akili Interactive Ltd.) that is the only FDA-approved game-based medical-software device so far and is intended for a different age group (children) and indication (attention deficit hyperactivity disorder, ADHD) (FDA, 2020; Kollins, 2018).

The study design includes primary-endpoint comparisons of the investigational device with both a comparator device and treatment as usual. On one hand, this aims to achieve strong evidence for our hypothesis about the therapeutic potential of specific

cognitive-training-related game mechanics. On the other hand, with the TAU arm, this design assesses the overall clinical relevance and value of MEL-T01 over the spectrum of currently available treatment-as-usual approaches. Finally, the comparison of MEL-S01 with TAU establishes the overall potential of “any” adaptive, closed-loop action-video-game based digital interventions to alleviate MDD symptoms.

The study design leverages randomisation of the subjects into three arms in blocks of six consecutive subjects. Randomisation is a robust and valid method that is typically used in clinical studies to acquire unbiased data. Randomisation in blocks further improves this by essentially eliminating the possibility that temporal variation in recruitment, such as some recruitment sources yielding more patients at some time than others, would bias the results. Possibilities of subject bias are limited by blinding both the subjects and the researchers from research arm randomisation and by using an active comparator that from the subject’s perspective is indistinguishable from the investigational device.

The rationale for choosing PHQ-9 as the outcome measure for the primary endpoint is that PHQ-9 has been proven to be a valid and reliable measurement of depression severity (Kroenke et al., 2001; Kroenke et al. 2002). In their meta-analysis, Manea et al. (2012) found PHQ-9 to have acceptable diagnostic properties for detecting MDD. In addition, PHQ-9 is mentioned by the Finnish Käypä Hoito for depression, and the questionnaire is widely used in Finland.

For the secondary endpoints, we sought to use clinical outcome measures that describe comprehensively the complex symptomatology of MDD. To corroborate our results with our primary outcome measurement, PHQ-9, we also employ another depression questionnaire (QIDS). As Finnish Käypä Hoito recommendation mentions, many patients that suffer from depression also suffer from anxiety (measured in our study by GAD-7), and we evaluate the potential of the interventions to influence symptoms of anxiety. Depression is also associated with rumination (measured in our study by RRS), that we hypothesise our intervention may reduce. Anhedonia, or the lack of positive emotions associated with depression (measured in our study by PVSS) may also be influenced. We also examine how depression influences disability in the subject’s everyday life (as measured by SDS) and measure the subjects’ general well-being (as measured by WHO-5). We also predict that the impact of our game is mediated by the degree the player immerses themselves into the game (as measured by IEQ).

Finally, the exploratory endpoints assess the post hoc comparability of patient cohorts and seek to identify factors mediating intervention success. These include substance abuse (as measured by ASSIST-LITE), post-traumatic stress disorder (measured in our study by PCL-5), and experiential avoidance, tendency to avoid negative experiences (measured in our study by BEAQ). We also evaluate whether the interventions influence game-addiction (measured in our study by GAS). For details regarding the clinical questionnaires, see section 3.6.5.1.

3.6.2 Investigational device and comparator

The investigational device MEL-T01 is a digital intervention based on an action-video-game-like software medical device for cognitive training (see 3.2). MEL-T01 and the active comparator MEL-S01 are similar with the exception that MEL-T01 includes real-time-strategy game mechanics and several forms of adaptive cognitive tasks, which have been removed from MEL-S01 (Table. 3). The absence of these game mechanics in MEL-S01 is accounted for by slight changes in enemy encounters in order to maintain as similar as

possible subject action levels and game pacing. The investigational device and comparator are thus very similar in terms of sensori-motor- and attentional-processing demands as well as engagement, arousal, reward processing, agency, narrative, and overall activation. This facet has been suboptimally realised in essentially all prior game-intervention research. Here, a rigorous comparator enables the possibility of drawing strong inferences about the mechanistic role of cognitive training in achieving the hypothesised therapeutic effect, thereby increasing the value of this investigation in forming a basis for future development of digital therapeutics for MDD and other brain disorders.

Table 3: Device features

Feature	Investigational device (MEL-T01)	Comparator (MEL-S01)
3D navigation	Yes	Yes
Gameplay tutorial	Yes	Yes
Enemy encounters	Yes	Yes
Narrative	Yes	Yes
Spellcasting	Yes	Yes
Environment interaction	Yes	Yes
Avatar abilities	Yes	Yes
Gameplay feedback	Yes	Yes
Avatar	Yes	Yes
Real-time strategy (RTS)	Yes	No
Cognitive tasks	Yes	No

3.6.3 Subjects

3.6.3.1 Inclusion criteria

Eligible subjects must fulfil all of the following criteria:

1. Between 18-65 year-old (self-reported)
2. Suffering from MDD (self-reported and corroborated by clinical interview, see 3.6.5.2.)
3. Have an ongoing mental health treatment contact to basic healthcare, specialised healthcare, student healthcare or occupational healthcare (self-indicated and confirmed by CSC)
4. Has sufficient eyesight with or without prescription (self-reported)
5. Has a Windows computer with internet connection and mouse (self-reported)
6. Has email and phone number (self-reported)

The subject MDD is indicated by a self-reported diagnosis and confirmed by a clinical MINI interview (see 3.6.5.2).

The criteria are also found in Appendix 1 - Rekrytointi-ilmoitus, which is given to the subjects. Only subjects who fulfil the inclusion criteria are admitted to study.

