The subjects ($N = 800$) volunteering to participate in this investigation are diagnosed with MDD and have an on-going mental health treatment contact with a mental health professional. The subjects are recruited through Helsinki and Uudenmaan sairaanhoitopiiri (HUS) psychiatry and Varsinais-Suomen sairaanhoitopiiri (VSSHP) psychiatry as well as online.

The subjects are randomised into three arms with equal probabilities in blocks of six consecutive subjects. Subjects in the MEL-T01 and MEL-S01 arms are engaged in the intervention for 12 weeks while those in the TAU arm are on a follow-up period during these 12 weeks.

After this 12-week period, the subjects in MEL-T01 and MEL-S01 arms enter a 12-week follow-up period and the subjects in TAU arm engage with either the MEL-T01 or MEL-S01 intervention (randomised at T0 with equal probability) for 12 weeks (See Table 1 below).

The subjects are recommended to play the investigational-device game for a total of 48 hours during the 12 weeks of active intervention with a recommended weekly dose of 4 hours. A minimum of 24 hours is needed for inclusion to hypothesis testing. The subjects are limited to a daily maximum of 1.5 hours of game time.

Prior to the intervention, a clinical interview (MINI) is performed via phone to confirm the subject's MDD diagnosis. The subjects' mental health symptoms and well-being are evaluated through online questionnaires five times: before subjects are randomised into one of the three groups (T0), and then 4 (T1), 8 (T2), 12 (T3), and 24 (T4) weeks after the study has begun.

Subject population:**Criteria for inclusion:**

Eligible subjects must fulfil all of the following criteria:

1. Between 18-65 year-old
2. Suffering from major depressive disorder
3. Have an ongoing mental health treatment contact to basic healthcare, specialised healthcare, student healthcare or occupational healthcare
4. Has sufficient eyesight with or without prescription
5. Has a Windows computer with internet connection and mouse
6. Has email and phone number

Criteria for exclusion:

Subjects who fulfil any of the following criteria are excluded from the study:

1. They have threat of self-harm
2. They have addiction to digital games
3. They have psychotic disorders
4. They are pregnant or breastfeeding
5. They have impaired ability in decision making
6. They are prisoner or forensic subject
7. They have neurological disorders such as epilepsy or brain injury

Safety assessments:

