3.3.2.2 Device stress under normal operating conditions

The device comprises client software at the subject's personal computer and backend software at the sponsor's backend servers.

The backend server capacity is sized to handle 100 times more concurrent patients than expected at any moment of this clinical investigation, and hence, under normal operating conditions, the backend stress is very unlikely to contribute to net device stress and its risk of failure.

The client software may face performance limitations depending on the CPU and GPU capacity of the subject's personal computer. When running in computers meeting the minimum specification, the client's performance is adequate to achieve the device's intended treatment outcome.

Device stress under normal operating conditions does not adversely affect the health or safety of the subject or any other persons.

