3.3.2.5 Compatibility

The investigational device's client application, *i.e.*, the "game" installed on the subject's personal computer, is compatible with the Windows operating system and a wide variety of hardware components as long as the minimum requirements are met. To ensure compatibility, it is advised to use a modern (purchased after 2010) computer with a separate graphics processing unit (GPU). Using an incompatible computer may lead to a compromised user experience or altogether prevent the playing of the game, but it does not cause any risks for the subject's health or safety.

Minimum requirements:

- CPU: Intel or AMD Quad-Core
- RAM: 4 GB
- OS: Windows 7
- VIDEO CARD: GeForce GTX 260 (1 GB) or Radeon HD 4850 (1 GB)

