3.3.2.7 Diagnostic or measuring functions

The device does not have diagnostic functions. The device has measuring functions for the subject's cognitive performance evaluation and adaptation of the game to the subject's individual performance level and changes therein. The measuring functions are designed in such a way that they are not compromised by usage of low performing personal computers as long as the minimum requirements are met.

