3.11 Accountability

3.11.1 Control of access to the device

Access to the software is only available as long as the digital key is valid. The digital key can be activated and deactivated remotely by the researchers. Only one install is possible with one digital key. Deactivated key prevents launching the software. The researchers can deactivate the subject's key if the subject doesn't follow the researchers instructions. Access to the game requires login to the distribution channel (Steam) and login to the game client itself.

Access to the MEL-T01 and MEL-S01 software is restricted to subjects who have completed the signup pipeline, T0 questionnaires, and gone through the clinical interview by the CSC. After this, the subjects are randomised to one of the three groups.

Whether in TAU, MEL-T01, MEL-S01 group, the access to the training is 12 weeks from the beginning of the intervention. For 2 weeks after the intervention has ended, the access to the training is denied from the user, but they can access the main menu through which they can complete the questionnaire T3 (groups MEL-T01 and MEL-S01) or T4 questionnaire (TAU group).

After the two weeks are over, the access to the software is denied, and the subject can uninstall it from their device. See Table 6 for a detailed outline of the access to the device.

Table 6: Access to the device

Access to the device											
Study arms	T0 (Before playing)	T1: T0 + 4 weeks	T2: T0 + 8 weeks	T3: T0 + 12 weeks	T3 + 2 weeks	T4: T0 + 24 weeks	T4 + 2 weeks.	After T4 + 2 weeks			
MEL-T01 intervention	T0 begins after CSC confirms the subject is eligible to the study. The subject is randomised to one of the three groups.	MEL-T01 intervention				Access to menu only.	No access to the device.				
MEL-S01 intervention		MEL-S01 intervention				Access to menu only.	No access to the device.				
Treatment as usual ("TAU")		Treatment as usual				Access to MEL-T01 or MEL-S01 intervention		Access to menu only.	No access to device.		

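### Inclusion criterion 5 omits the device's own minimum hardware specification, so people whose computers cannot run the game can be randomised and then excluded from the game arms only

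*Combined protocol and SAP*

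**What the plan says.** **Eligibility.** Criterion 5 in section 3.6.3.1 is "Has a Windows computer with internet connection and mouse (self-reported"). The synopsis (3.1.6) has the same content: "Has a Windows computer with internet connection and mouse". Neither mentions processor, memory, operating-system version or graphics card.

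**What the device needs.** Section 3.3.2.5 lists minimum requirements, among them "CPU: Intel or AMD Quad-Core" and "VIDEO CARD: GeForce GTX 260 (1 GB) or Radeon HD 4850 (1 GB"), with 4 GB of RAM and Windows 7. A separate graphics unit is advised there. The section adds: "Using an incompatible computer may lead to a compromised user experience or altogether prevent the playing of the game".

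**What rests on the minimum.** Section 3.3.2.2 calls client performance adequate for the intended treatment outcome "When running in computers meeting the minimum specification". Section 3.3.2.7 says the measuring functions that drive adaptation are not compromised on weak computers "as long as the minimum requirements are met".

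**Order of events.** Section 3.11.1 makes the software available to subjects who have finished sign-up, the T0 questionnaires and the clinical interview, then states: "After this, the subjects are randomised to one of the three groups". Section 3.10.1 gives the same order, with access for the two game arms following randomisation. TAU subjects receive a game only after T3.

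**Analysis rule.** Section 3.7.2 requires at least 24 hours of play within the 12 weeks and excludes subjects who do not meet its criteria.

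**The concern.** Whether a computer can run the game is a fact about the subject that could be established before allocation. As written, the plan lets it show itself afterwards. In MEL-T01 and MEL-S01 the subject cannot start, or plays poorly, and is likely to miss the 24-hour threshold. In TAU the same subject has no contact with the software before T3 and can supply complete T0 and T3 scores.

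The TAU arm would then keep a group of people that both game arms have lost. Owners of older or weaker computers may differ in age, income, employment or severity of illness. The documents do not say whether they do, but randomisation no longer protects against it once they are removed from one side. Two of the three primary comparisons, each game against TAU, are exposed.

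There is also a smaller matter. Subjects below specification who do manage to play fall outside the conditions under which 3.3.2.2 and 3.3.2.7 give their assurances about performance and adaptation.

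**Working it through.** **Step 1. Can someone below specification satisfy every written criterion?** Set 3.6.3.1 beside 3.3.2.5:

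| Item | Criterion 5 | Minimum in 3.3.2.5 |
|---|---|---|
| Operating system | Windows, version not stated | Windows 7 |
| Processor | not stated | quad-core |
| Memory | not stated | 4 GB |
| Graphics | not stated | GTX 260 or HD 4850, 1 GB |
| Internet, mouse | required | not listed |

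Yes. A Windows computer that misses the processor, memory or graphics line still meets criterion 5.

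**Step 2. Does any described step catch it before allocation?**
- Sections 3.6.3.3 and 3.6.5.2: the coordinator's call confirms the listed criteria, which contain no specification.
- Section 3.7.1.1: sign-up collects contact details, demographics, mental-health history, gaming history and interest in the interview and sub-study. Hardware is not named.
- Sections 3.10.1 and 3.11.1: the game is released after randomisation.

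None of these is a hardware check. The detailed questions are in Appendices 1, 5 and 7, which were not supplied.

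**Step 3. What happens in the primary analysis?** Under 3.7.2, a game-arm subject who cannot play has under 24 hours and is excluded. For TAU the section is not explicit. Read literally, 24 hours of play during the first 12 weeks would exclude all of TAU. The interim rule (3.7.5), however, needs 33 TAU subjects who qualify once those 12 weeks are complete, and 3.6.4.3 says those weeks are follow-up for TAU. The workable reading is that the rule does not bind TAU for T0 to T3. That is an inference, and the arm difference depends on it.

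**Step 4. The plan's sample size.** Inputs from 3.7.4.1: d = 0.40, alpha 0.0167 two-sided, power 0.80, 1:1:1 allocation. A two-sample t-test (noncentral t) gives 132.2, rounded up to 133 per arm, with power 0.803 at 133. Then 3 × 133 = 399, rounded to 400, and 400 / 0.50 = 800. The plan's figures reproduce, and this point does not change them.

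**Step 5. How many subjects?** The documents give no rate of incompatible computers. Let f be an assumed share who cannot play. Randomised per arm: 800 / 3 = 266.7, about 267. Unable to play per game arm = 266.7 × f:

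| Assumed f | Per game arm | Both game arms |
|---|---|---|
| 5% | 13.3, about 13 | 26.7, about 27 |
| 10% | 26.7, about 27 | 53.3, about 53 |
| 20% | 53.3, about 53 | 106.7, about 107 |

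A similar number would be expected in TAU, but they would stay in the analysis under the reading in Step 3.

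**The case against.** **Power.** A reader might infer that non-players dilute d = 0.40 and so cost power at 133 per arm. With zero effect in 5%, 10% or 20% of subjects, d becomes 0.38, 0.36 or 0.32. The documents do not support evaluating these at 133. Section 3.7.4.2 counts the 133 as subjects who already meet 3.7.2, so someone who cannot play is never among them, and recruitment stays open until 133 per arm qualify. If everyone randomised were kept instead, n would be about 267 per arm. Power at the three diluted effects would then be 0.976, 0.960 and 0.902, assuming no missing outcomes. The 50% dropout allowance may also absorb the loss. This objection stands in full.

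**Certainty.** It is tempting to say that incompatibility is found only after randomisation. The body text shows no earlier check, but the recruitment notice, call script and question list were not available and could contain one. This stands as a limit. Even so, 3.6.3.1 says Appendix 1 carries these same criteria, and a question without a criterion would make nobody ineligible.

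**Below specification is not the same as untreatable.** Section 3.3.2.5 allows for compromised use as well as no play. A separate graphics unit is only advised. Section 3.3.2.2 makes the specification sufficient for adequate performance; it does not say the treatment fails below it. The advised computer is one bought after 2010, a modest demand for a trial planned to start in 2022. All of this stands, and it means the number truly unable to play could be small.

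**Other causes.** The 24-hour rule removes low users for any reason, and hardware is only one. That is correct. It limits what the fix achieves, but it is no reason to leave a preventable part in place.

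**Conclusion.** The point holds as a mismatch with a cheap remedy. Criterion 5 admits people whose computers fall below the device's stated minimum, and the CIP body describes no step that would identify them before allocation. Those who cannot run the game are certain to be excluded from the game arms under 3.7.2. This adds a post-randomisation exclusion to MEL-T01 versus TAU and MEL-S01 versus TAU. One specification is given for both games, so MEL-T01 versus MEL-S01 should be affected about equally.

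The size is not known. The 13, 27 or 53 subjects per game arm rest on assumed shares of 5%, 10% and 20%, on 800 being randomised equally, and on those subjects being unable to play at all. The difference between arms rests on the 24-hour rule not being applied to TAU for T0 to T3. The direction of any bias cannot be told from the documents. No power loss and no change to the sample size follow.

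**What to change.** Reword criterion 5 in 3.1.6, 3.6.3.1 and Appendix 1 so that it requires a Windows computer meeting the minimum in 3.3.2.5, with internet connection and mouse. Confirm this before randomisation for every subject, whichever arm follows. Either of two ways will do: a sign-up field for processor, memory, operating system and graphics card, or a short hardware check with no game content. Subjects who fail are not randomised. If an appendix already asks for this, cite it in 3.6.3.3 and tie it to the criterion.

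The cost is amendment wording plus one sign-up item or a small checking tool. There will be some additional screen failures, including a few people below specification who might have managed to play. The change takes the same people out of all three arms before allocation. It does not remove the wider selection created by the 24-hour rule, which needs its own treatment, and 3.7.2 should in any case state how that rule applies to TAU.

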3.6.3.2 Exclusion criteria

Subjects who fulfil any of the following criteria are excluded from the study:

1. They have a threat of self-harm (evaluated by the clinical interview, see 3.6.5.2.)
2. They have an addiction to digital games (self-reported)
3. They have psychotic disorders (self-reported)
4. They are pregnant or breastfeeding (self-reported)
5. They have impaired ability in decision making (self-reported)
6. They are prisoner or forensic subject (self-reported)
7. They have neurological disorders such as epilepsy or brain injury (self-reported)

Should the subject indicate that they have suicidal thoughts, they are evaluated by the clinical subject coordinator in the clinical interview for the severity of suicidality. If the subject has a threat of harming themselves (See 3.6.5.2 for procedures), they are excluded from the study.

The criteria are also found in Appendix 1 - Rekrytointi-ilmoitus which is given to the subjects. Only subjects who do not fill the exclusion criteria are admitted to study. To further ensure that the subjects do not meet the exclusion criteria, we contact them through the phone prior to the intervention.

The exclusion criteria are compliant with the law concerning medical research in Finland (Laki lääketieteellisestä tutkimuksesta, 9.4.1994/488; 2 luku) with respect to specific protected categories of subjects:

- Elderly (2 luku, §7)
- Underaged (2 luku, 8 §)
- Those with impaired ability to make decisions (“vajaakykyinen”), (2 luku 7 §)
- Those pregnant or breastfeeding (2 luku, 9 §)
- Prisoners or forensic psychiatric subjects (2 luku, 10 §)

